1.6 Secondary Specific Aim

- Demonstrate that the use of the SI-informed smart bolus calculator in an HCL system provides increased protection against hypoglycemia.

229 **Chapter 2: Study Devices**

230 **2.1 Insulin Pump**

231 The study system will include the Tandem t:ap research pump connected to the UVA DiAs system
232 running on a dedicated external smartphone, implementing either the USS Virginia algorithm
233 alone or the USS Virginia algorithm with the smart bolus calculator.

234 **2.2 Continuous Glucose Monitor**

235 The study CGM will include Dexcom G6 transmitter and sensors. The CGM sensor is viable for 10
236 days. Like the insulin pump, the CGM system will be connected to DiAs.

237 **2.3 Blood Glucose Meter and Strips**

238 Upon need, blood glucose levels will be measured using the study blood glucose meter
239 (glucometer). The CGM device will be calibrated, if needed, using the study glucometer and strips
240 in accordance with the manufacturer's labeling. Glucometers will be available during the study
241 admission(s).

242 **2.4 Ketone Meter and Strips**

243 Upon need, blood ketone levels will be measured using the Abbott Precision Xtra meters and
244 strips in accordance with the manufacturer's labeling. The blood glucose meter component of
245 the Precision Xtra Device will not be used. Ketone meters will be available during the study
246 admission(s).

247 **2.5 Study Devices Accountability Procedures**

248 Device serial numbers will be recorded, and use of equipment will be tracked.

249 **Chapter 3: Study Screening**

250 **3.1 Participant Recruitment and Enrollment**

251 Participants will be recruited from the UVA Center for Diabetes Technology registry, social media
252 advertisements, physician contacts at pediatric diabetes clinics in Virginia, and previous camp
253 attendance data. The enrollment goal in the pilot study will be to complete up to three
254 participants. Up to four participants may sign consent/assent forms. The enrollment goal for the
255 main study is to complete 30 participants. Up to 70 participants may sign the consent form.

256 **3.2 Informed Consent and Authorization Procedures**

257 Before consent has been obtained, participants will be asked inclusion/exclusion criteria
258 questions during prescreening to determine study eligibility. Before completing any procedures
259 or collecting any data that are not part of usual care, written informed consent will be obtained.

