407 Dexcom Share App for monitoring for the at-home use of the CGM. A study phone may be
408 provided for this purpose.

409 **5.2 Study Insulin Pump**

410 The study team will be responsible for monitoring and managing the study insulin pump during
411 the study admission(s). The participants will be provided a quick overview on its functionality.

412 **5.2.1 Study Insulin Pump Topics**

413 The study team will assist the participant in placing the study pump infusion site and will start
414 the participant on the study pump. The study pump will be programmed by the study staff based
415 on the participant's home parameters, with a 10-20% reduction of basal rate determined by the
416 study physician to account for increased physical activity at the camp. The participant's personal
417 pump and infusion site will be removed.

418 The participant will be instructed on placing infusion sites, cartridge/priming procedures,
419 charging the pump, navigation through menus, and bolus procedures including stopping a bolus,
420 etc.

421 **5.2.2 Other Issues**

422 The participant will be instructed to notify study staff if they experience any issues with the study
423 devices during the study admission(s). Staff will be present in the event that insulin is delivered
424 by any means other than the study pump (e.g., injection of subcutaneous insulin via syringe in

CLINICAL PROTOCOL

425 the event of infusion site failure). If insulin is delivered by any means other than the study pump,
426 closed-loop mode will be turned off for approximately four hours.

427 The participant will be asked to alert the study clinical staff for any illness that develops during
428 use of the study system. Participants will also alert the study staff for any technical issues or
429 component disconnections with the study pump and/or the DiAs system.

430 A glucagon emergency kit will be available at all times during the study for use during
431 emergencies. Glycemic Treatment Guidelines will be available for staff to use during the camp.

432 **5.2.3 Optimization of Insulin Pump Settings**

433 Optimization of pump settings can occur at any time during the study per the discretion of the
434 study physician if there are concerns regarding recurring hypo- or hyperglycemia.

435 **Chapter 6: Pilot Study**

436 The Pilot Study will be performed at a local hotel. The study admission will take up to 24 hours

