- 563 • Confirm that the participant brought his/her personal insulin and regular medications.
- 564 • Participants will be asked to perform a blood ketone fingerstick. If ketones are not <0.6
565 mmol/L, study staff should treat with oral hydration and, if needed, the Glycemic
566 Treatment Guidelines will be followed; ketones will be re-checked every hour until <0.6
567 mmol/L. The participant will be able to begin participation in the camp activities once the
568 CGM reads between 80-250 mg/dL and ketones are <0.6 mmol/L.

569 **8.3.2 Assignment to Randomization Group**

570 Participants will be placed on the study CGM and insulin pump and the DiAs system implementing
571 the algorithm of the specific arm (experimental or control) will be connected to the participant's
572 CGM transmitter via Bluetooth connection. The study team will ensure the proper functioning of
573 the CGM and insulin pump.

574 **8.4 Main Admission(s) Activities and Procedures**

575 **8.4.1 General Admission(s) Overview**

576 During the entire duration of each study admission(s), the study team will remotely monitor
577 participants' real-time CGM readings. Study team members trained in all protocol interventions
578 (including the hypoglycemia and hyperglycemia safety protocols) will be with the participants at
579 all times during camp activities, with each member remotely connected to the participants CGM
580 data. In addition, a study team physician trained in all protocol and glycemic treatment guideline
581 procedures will be available at a central location on camp property.

582 All recreational activities will be managed by the staff and counsellors at Camp Holiday Trails with
583 study staff supervision.

584 During the overnight hours, study staff will be actively monitoring real-time CGM data for all
585 participants with direct access to the participants.

586 **8.4.2 Device Procedures for Participants**

587 The study insulin pump and DiAs device will be provided upon arrival to the camp. All participants
588 will continue to wear the study CGM. When participants crossover into the other treatment
589 group, they will continue to wear the same study CGM and study insulin pump with the change
590 only made to the software that the system is running.

CLINICAL PROTOCOL

591 Participants will have all equipment with them at all times. Study staff will be available at all times
592 to assure proper use of all study equipment.

593 **8.4.3 Meal Requirements**

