672 If the CGM signal becomes unavailable for more than 20 minutes consecutively, the HCL system
673 will not operate to automatically adjust insulin. If the CGM is not connected, the system will
674 revert to usual function of the pump and deliver insulin with the insulin dosing parameters
675 programmed in the system for that individual. Resumption of Closed-Loop will
676 occur automatically once CGM signal is available again. If the study system is unable to activate
677 HCL for any reason, the pump will automatically revert to pre-programmed basal insulin delivery

CLINICAL PROTOCOL

678 without any need for instruction from the user. Study staff will be available at all times to assist
679 with any issues in connectivity that arise.

680 **Chapter 9: Testing Procedures**

681 **9.1 Laboratory / Point of Care Testing**

682 **9.1.1 HbA1c**

- 683
 - HbA1c level may be measured by study team using the DCA2000, a comparable point
- 684
 - of care device at study admission #1.

685 **9.1.2 Pregnancy Test**

- 686
 - Pilot study admission: A urine pregnancy test will be required for women who are in
- 687
 - childbirth potential at the study admission. Test must be negative to participate in the
- 688
 - study.
- 689
 - A urine pregnancy test will be required for women of childbearing potential at the
- 690
 - time of study admission(s). Test must be negative to participate in the study.

691 **9.1.3 COVID-19 Test**

- 692
 - Main study admission(s): A COVID-19 PCR test will be required for participants and
- 693
 - staff 48-72 hours prior to the study admission(s). Participants and staff with a positive
- 694
 - test result within 10 days of the camp will be excluded from the study admission(s).
- 695
 - Any appearance of COVID-19 symptoms in participants or staff members after the
- 696
 - mandatory pre-admission COVID-19 PCR test will result in discharge from the study
- 697
 - admission(s).

698 **Chapter 10: Risks Associated with Clinical Trial**

699 **10.1 Potential Risks and Benefits of the Investigational Device**

700 Risks and Benefits are detailed below. Loss of confidentiality is a potential risk; however, data are
701 handled to minimize this risk. Hypoglycemia, hyperglycemia and ketone formation are always a
702 risk in participants with T1D and participants will be monitored for these symptoms.

703 **10.1.1 Fingerstick Risks**

704 About 1 drop of blood will be removed by fingerstick for measuring blood sugars and sometimes

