- 1187 • percentage of time spent in 70-140 and 70-180 mg/dL
- 1188 • percentage of time spent above 180 and 250 mg/dL
- 1189 • the high blood glucose index

CLINICAL PROTOCOL

- 1190 • average CGM
- 1191 • CGM coefficient of variation
- 1192 • Total number and amount of carbohydrate administered as rescue treatments

1193 All glycemic outcomes (primary efficacy endpoint and secondary outcomes) will be computed
1194 based on CGM records. The primary analysis will focus on the postprandial period, but other
1195 analyses will evaluate different time intervals to assess whether the impact on the postprandial
1196 period will be influential enough to impact the overall daily control. Paired t-tests or non-
1197 parametric Wilcoxon signed-rank tests will be used to compare the control and experimental
1198 arms on the different glycemic outcomes, in case of normally/non-normally distributed samples
1199 respectively (Shapiro-Wilk test). Significance level will be set at a P value less than 0.05. All
1200 statistical analyses will be computed in SPSS Statistics 26 (IBM).

1201 **13.4 Safety Analyses**

1202 Safety endpoints are secondary outcomes addressing hypoglycemia and hyperglycemia, i.e.,
1203 percentage of time below 70 mg/dL and above 250 mg/dL, and total number and amount of
1204 carbohydrate administered as rescue treatments.

1205 **13.5 Baseline Descriptive Statistics**

1206 Baseline demographic and clinical characteristics of the cohort of all randomized participants will
1207 be summarized in a table using summary statistics appropriate to the distribution of each
1208 variable. Descriptive statistics will be displayed overall and by treatment group.

1209 Will include:

- 1210 • Age
- 1211 • HbA1c
- 1212 • Gender
- 1213 • Race/ethnicity
- 1214 • Diabetes duration
- 1215 • BMI

1216 **13.6 Device Issues**

1217 The following tabulations and analyses will be performed by treatment group to assess device
1218 issues:

- 1219 • Device malfunctions requiring study team contact and other reported device issues

CLINICAL PROTOCOL

- 1220 • Sensor performance metrics (difference, absolute relative difference, and
1221 International Organization for Standardization criteria) – if applicable, by sensor
1222 version.
- 1223 • % time CGM data available - overall and by month
- 1224 The following tabulations will be performed for the Experimental arm only:
- 1225 • Performance metrics, describing the CLC system and its components like:

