- 1226 a. % time CGM data were available to the CLC system – overall and by month
- 1227 b. % time in different operational modes per week - overall and by month
- 1228 c. Rate of different failure events and alarms per 48 hours recorded by the CLC
1229 system – overall and by month

1230 **Chapter 14: Data Collection and Monitoring**

1231 **14.1 Case Report Forms and Device Data**

1232 The study data are collected through a combination of case report forms (electronic and paper)
1233 and electronic device data files obtained from the software and individual hardware
1234 components. These electronic device files and electronic CRFs are considered the primary source
1235 documentation.

1236 When data are directly collected in electronic case report forms, this will be considered the
1237 source data. Records will be maintained in accordance with ICH E6 and institutional regulatory
1238 requirements for the protection of confidentiality of participants.

1239 **14.2 Study Records Retention**

1240 Study documents should be retained for a minimum of 2 years after the last approval of a
1241 marketing application in an ICH region and until there are no pending or contemplated marketing
1242 applications in an ICH region or until at least 2 years have elapsed since the formal
1243 discontinuation of clinical development of the investigational product. These documents should
1244 be retained for a longer period, however, if required by local regulations. No records will be
1245 destroyed without the written consent of the sponsor, if applicable. It is the responsibility of the
1246 sponsor to inform the investigator when these documents no longer need to be retained.

1247 **14.3 Protocol Deviations**

1248 A protocol deviation is any noncompliance with the clinical trial protocol, Good Clinical Practices
1249 (GCP), or procedure requirements. The noncompliance may be either on the part of the
1250 participant, the investigator, or the study site staff. As a result of deviations, corrective actions
1251 may be developed by the site and implemented as appropriate. Major deviations will be reported
1252 to the IRB-HSR within 7 calendar days of when the study team becomes aware of the event.

CLINICAL PROTOCOL

1253 **Chapter 15: Ethics/Protection of Human Participants**

1254 **15.1 Ethics Standard**

1255 The investigator will ensure that this study is conducted in full conformity with Regulations for

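### Section 13.6 tabulates operating modes and system-logged failures and alarms for the experimental system only, although control is also closed loop, and uses week and month units for 2–3 days of use

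*Combined protocol and SAP*

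**What the plan says.** Section 13.6 (Device Issues) contains two lists.

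The first is by treatment group. It covers malfunctions and other reported device issues, sensor accuracy metrics, and the percentage of "time CGM data available - overall and by month".

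The second opens with "The following tabulations will be performed for the Experimental arm only" and has three closed-loop performance items:

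- (a) the percentage of time that CGM data reached the closed-loop system, overall and by month;
- (b) the percentage of "time in different operational modes per week - overall and by month";
- (c) "Rate of different failure events and alarms per 48 hours recorded by the CLC" system, again overall and by month.

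On what the two conditions share, section 2.1 describes one research pump connected to DiAs, "running on a dedicated external smartphone, implementing either the USS Virginia algorithm" with or without the smart bolus calculator. Section 8.4.2 says that at crossover "they will continue to wear the same study CGM and study insulin pump with the change" confined to the software. Section 13.1 names the control condition as the USS Virginia hybrid closed loop. Section 1.5 makes safety and feasibility of the calculator within such a system the primary aim.

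**The concern.** An experimental-only table of closed-loop performance suits a trial whose control group has no closed loop. Here both conditions run one. Operating modes, communication failures and alarms will therefore arise in the control periods too, from the same hardware and much of the same software.

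If only the experimental figures are shown, a given alarm rate or share of time out of closed loop cannot be attributed. It may come from the shared platform, from camp conditions or from the added calculator. A crossover design is well placed to make that distinction, because each participant uses both systems.

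Separately, the weekly and monthly breakdowns look as if they belong to a longer study.

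**Working it through.** **1. Which items have a comparator under 13.6 as written**

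| Item | Control figures planned? |
|---|---|
| Reported malfunctions and device issues | Yes |
| Sensor metrics | Yes |
| % time CGM available | Yes |
| (a) % time CGM data reached the closed-loop system | No, but largely the same as the line above |
| (b) Time in each operating mode | No |
| (c) System-logged failures and alarms | No |

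The gap is therefore chiefly b and c.

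**2. Whether the by-group tables can stand in for b and c**

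*Reported device issues for c.* Section 11.8 exempts several anticipated problems from reporting, among them component disconnections and intermittent communication failures that do not lead to system replacement. The by-group table of reported issues will miss these. A log-based count such as item c could capture them.

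*CGM availability for b.* The two measures differ in both directions.
- Loop on, CGM missing: section 8.7 stops automatic adjustment only after a longer gap ("If the CGM signal becomes unavailable for more than 20 minutes consecutively, the HCL system" stops adjusting). Shorter gaps reduce CGM availability but not closed-loop time.
- Loop off, CGM present: after insulin is given other than by the study pump, "closed-loop mode will be turned off for approximately four hours" (5.2.2). Section 8.7 also provides for reversion to programmed basal delivery whenever closed loop cannot be activated.

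So CGM availability is neither an upper nor a lower bound on closed-loop time.

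**3. Hours per participant on each system (8.4.4, with discharge times from 8.5)**

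- Weeklong camp, first period: from 1300–1600 on the check-in day to about 0800 on Day 3. From 1600: 72 + 8 − 16 = 64 h. From 1300: 72 + 8 − 13 = 67 h.
- Weeklong camp, second period: from about 0800 on Day 3 to Day 5. To 0800 (breakfast): 48 h. To the earliest discharge at 0900: 49 h. To 1200: 52 h.
- Each long weekend: from 1300–1600 on the first day to 0900–1200 on the fourth. Shortest: 72 + 9 − 16 = 65 h. Longest: 72 + 12 − 13 = 71 h.

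The overall range is 48–71 h, or 2.0–3.0 days.

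**4. Whether the units fit**

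- Week: 48/168 = 29% and 71/168 = 42%. No participant completes a week on a system.
- Month (30.4 days, 730 h): 48/730 = 7% and 71/730 = 10%.
- 48 hours: 48/48 = 1.0 and 71/48 = 1.5 intervals. This unit fits.

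'Per week' is attached to item b only. 'By month' is attached to a, b and c and to the by-group CGM line.

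**5. Amount of data per system, for 30 participants (15 per order)**

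- Weeklong camp: 15×64 + 15×48 = 1,680 h to 15×67 + 15×52 = 1,785 h. Divided by 48, this is 35–37 blocks of 48 h.
- Two weekends: 30×65 = 1,950 h to 30×71 = 2,130 h, or 41–44 blocks.

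In the weeklong camp the first period is 64/52 = 1.2 to 67/48 = 1.4 times as long as the second. Tables by period therefore need hours on the system as the denominator.

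**6. Sample size**

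The figure in 13.2 reproduces: an exact two-sided paired t-test with d_z = 0.614 and α = 0.05 needs n = 30, with power 0.901. Nothing above enters that calculation.

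**The case against.** The strongest reply is that 1.5 asks for feasibility of using the calculator over several days and meals, and does not ask for a comparison. A description of the experimental system answers that wording, and 13.6 is headed as device issues, not as the feasibility analysis. This stands in part: the plan does not contradict itself. But a description of one system cannot separate what the calculator adds from what the shared platform already does, and the data for that contrast should arise anyway.

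It can also be said that every affected line asks for an overall figure, so the odd units cost little, and that 'by month' might mean calendar month across camp sessions. The first is right and makes the units an editorial matter. The text does not support or exclude the second, and a calendar split would not describe time on a system.

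Four stronger readings are tempting, and the documents do not support them.

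- *That 13.6 has no comparator at all.* Its first list is by treatment group.
- *That the primary endpoint is compromised.* The closed-loop-off spell in 5.2.2 is about as long as the four-hour post-dinner window in 13.3.1, so a reader might infer a threat to LBGI. The documents give no frequency for insulin given outside the pump and nothing to place it after dinner. Tables by system and period would not show loop status after dinner either.
- *That a control column would reveal a doubling of alarms.* No alarm rate is given. Assume 0.5 per 48 h on control and 35 blocks: 17.5 against 35 expected events. The SE of the log ratio is √(1/17.5 + 1/35) = 0.293, and power is Φ(0.693/0.293 − 1.96), about 66% for independent Poisson counts. With twice the Poisson variance (assumed) it is about 39%. At an assumed 2 per 48 h (70 against 140 events, SE 0.146) it exceeds 99%. The answer depends on an unknown rate.
- *That 'arm' might mean treatment order.* Section 13.1 uses the word that way once, but 8.3.2 and 13.3.2 speak of experimental and control arms. The restriction has one sensible reading.

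**Conclusion.** The point holds as a gap in descriptive reporting. Followed as written, 13.6 gives operating modes and system-logged failures and alarms for one of two closed-loop systems that share DiAs, pump and CGM. The by-group tables do not fill that gap. The plan therefore cannot show whether these measures differ with the calculator added, which limits the feasibility conclusion under 1.5.

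The week and month units do not fit 48–71 h per participant per system. That part is minor.

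The primary LBGI test and N = 30 are unaffected. The hours assume that the estimated itinerary times are kept. The value of the added columns assumes that the device files record modes and alarms in the control periods as well. That is an inference from the shared platform, and the documents do not state it.

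**What to change.** In 13.6:

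- Produce items a–c for both systems, descriptively, by system in use and by treatment period.
- Report each item overall, and failures and alarms per 48 hours, with hours on the system as the denominator.
- Delete 'per week' from item b, and 'by month' from items a–c and from the by-group CGM line.

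The cost is a few more table columns. Sample size, visits, tests and blinding do not change. Section 14.1 already provides for electronic files from the software and hardware components. Before the tables are programmed, the sponsor should confirm that these files hold mode and alarm records for both systems.
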